3.1. Subject Inclusion Criteria

Subjects must meet all of the following inclusion criteria to be eligible to enroll in this study:

1. Provide signed and dated informed consent. For Part A only: signed pre-screening consent for subjects that undergo pre-screening procedures or collection of historical data prior to informed consent procedure.
2. Male or female aged ≥ 18 years.
3. Subjects with histologically or cytologically confirmed/documented diagnosis of advanced-stage, relapsed/refractory solid tumors in non-curable state as per current clinical knowledge.
4. For Part A (Phase 1), subjects must have received during their prior treatment at least one anti-PD-1/PD-L1 treatment (alone or in combination) and progressed on or relapsed after completion of the anti-PD-1/PD-L1 treatment (with a minimum of 12 weeks of anti-PD-1/PD-L1 exposure).

For Part B (Phase 2a), subjects must either have

(1) bladder cancer, hepatocellular cancer, non-small cell lung cancer, cutaneous squamous-cell carcinoma, or melanoma (for melanoma, only cutaneous and mucosal forms, not uveal/ocular) (approved anti-PD-1/PD-L1 indications) that relapsed on or were primary refractory to prior anti-PD-1/PD-L1 therapy with an approved anti-PD-1/PD-L1 compound (with a minimum of 12 weeks of anti-PD-1/PD L1 exposure).

For cutaneous squamous-cell carcinoma, subjects have to have locally advanced disease or metastatic disease. Cutaneous squamous-cell carcinoma subjects with locally advanced disease must not be candidates for surgery for one or both of the following reasons: disease recurrence after two or more surgical procedures and as per treating physician curative resection is unlikely or surgery would result in substantial complications or deformity.

(2) colorectal cancer (MSS/mismatch-repair competent) and have not received any prior anti-PD-1/PD-L1 therapy

(3) biomarker cohort with mixed solid tumors (“basket” cohort) that relapsed on or were primary refractory to prior anti-PD-1/PD-L1 therapy with an approved anti-PD-1/PD-L1 compound and that have exhausted available approved therapies for their disease or do not qualify for them anymore.

Note: All Subjects in cohorts (1) and (3) must have received an approved anti-PD-1/PD-L1 compound with a minimum of 12 weeks of anti-PD1/PD L1 exposure. Non-approved, experimental anti-PD-1/PD-L1 treatments are not permissive for enrolment into this group (does not apply for other cohorts).

5. Ability to understand the purpose of the study, provide signed and dated informed consent prior to performing any protocol-related procedures (including Screening evaluations), and able to comply with the study procedures and any locally required authorization.
6. For Part A, ideally ~50% of subjects enrolled per dose level should have increased GDF-15 serum levels (based on pre-screening result or historic serum GDF-15 data [up to 2 months prior to the start of treatment with CTL-002 where available]).
7. All subjects must have biopsy-accessible tumor lesions and be willing to undergo tumor biopsy: triple sequential biopsies (Part A) or dual-sequential biopsies (Part A backfill); in Part B, baseline biopsy (new or archived if obtained within 120 days prior to treatment start) from all subjects. For melanoma, cutaneous squamous-cell carcinoma and the biomarker cohort with mixed solid tumors (“basket” cohort) an additional on-treatment biopsy is mandatory. All biopsies are mandatory unless not seen as safe and feasible by the treating physician or another specific reason that precludes a biopsy sample being taken and which should be discussed with the Medical Monitor prior to Screening or if applying to the sequential biopsy, prior to that biopsy. All other study eligibility criteria must be met before the baseline biopsy sample is obtained.
8. For Part B, presence of radiologically measurable disease at baseline – with at least 1 lesion, not previously irradiated, that can be accurately measured at baseline as ≥ 10 mm in the longest diameter with computed tomography (CT) or magnetic resonance imaging (MRI) and is suitable for accurate, repeated measurements as per RECIST V1.1/iRECIST is required. This shall not be the lesion that is going to be biopsied.
9. ECOG Performance Status 0-1.
10. Life expectancy >3 months as assessed by the Investigator.
11. Adequate organ function:
 - a. Bone marrow function: hemoglobin ≥ 9.0 g/dL (equal to 5.59 mmol/L); platelet count $\geq 100 \times 10^9$ /L; leukocyte count $\geq 2.5 \times 10^9$ /L.
 - b. Hepatic function: AST and ALT $\leq 2 \times$ upper limit of normal (ULN) ($3 \times$ ULN in the case of liver metastases); bilirubin $\leq 1.5 \times$ ULN ($2 \times$ ULN in case of liver metastases/subjects with Gilbert’s disease).
 - c. Renal function: serum creatinine $< 1.5 \times$ ULN and/or creatinine clearance ≥ 50 ml/min (Cockcroft-Gault equation).
 - d. Coagulation: no evidence for clinically relevant hypo- or hypercoagulability or presence of thrombosis/thrombotic event as per D-Dimer, antithrombin III (ATIII), prothrombin time (PT)/international normalized ratio (INR), and activated partial thromboplastin time (aPTT) analysis and treating physician’s assessment.
12. All toxicities related to prior radiotherapy, chemotherapy, and any type of immunotherapy or other anti-cancer therapy, or surgical procedure must have recovered to Grade ≤ 1 based on NCI-CTCAE v5.0, except alopecia (any grade), and Grade 2 peripheral sensory neuropathy, and AEs that are clinically not considered as significant in this context and/or are stable on supportive therapy.
13. If subject has type II diabetes and receives metformin, metformin has to be replaced with other antidiabetic(s) prior to start of study treatment (at minimum 7 days prior to study baseline GDF-15 measurement) and for the whole study treatment duration.
14. Women of childbearing potential must have a negative serum pregnancy test within 7 days

prior to CTL-002 treatment. If a pregnancy test is not performed within 7 days of dosing with CTL-002, a repeat test must be performed prior to Day 1 dosing.

Women of childbearing potential are defined as sexually mature women without prior hysterectomy or who have had any evidence of menses in the past 12 months. However, women who have been amenorrheic for 12 or more months are still considered to be of childbearing potential if the amenorrhea is possibly due to prior chemotherapy, anti-estrogens, or ovarian suppression.

15. All subjects, male and female, who are not surgically sterilized or postmenopausal as defined above, and subjects' partners of childbearing potential must agree to use "highly effective methods of contraception" during the study and for at least 5 months (5 times the predicted half-life of CTL-002 in humans) after the last dose of CTL-002.

"Highly effective methods of contraception" are combined (estrogen and progestogen containing) hormonal contraception associated with inhibition of ovulation, progestogen-only hormonal contraception associated with inhibition of ovulation, intrauterine device, intrauterine hormone-releasing system, bilateral tubal occlusion, vasectomized partner, or sexual abstinence.

The double-barrier method (synthetic condoms, diaphragm, or cervical cap with spermicidal foam, cream or gel), periodic abstinence (such as calendar, symptothermal, or post-ovulation), withdrawal (coitus interruptus), lactational amenorrhea method and spermicide only are NOT acceptable as "highly effective methods of contraception."

3.2. Subject Exclusion Criteria

Subjects meeting any of the following exclusion criteria are not eligible to enroll in this study:

1. Pregnant or breastfeeding.
2. Has received any tumor-directed therapy within 21 days before start of study treatment.
3. Treatment with any investigational agent within 21 days before start of study treatment.
4. Radiotherapy within 14 days before the start of the study treatment; however, subjects may receive palliative radiotherapy upon discussion and approval from the Medical Monitor if needed on non-target lesions.
5. Any acute or chronic major tissue injury that may require maintained GDF-15 function for tissue protection as per Investigator assessment (diagnosed with liver, kidney, myocardial infarction, or other major organ failure, all within < 6 months prior to Screening).
6. Pre-existing arrhythmia (unless considered clinically not relevant), uncontrolled angina pectoris, diagnosed with heart failure New York Heart Association (NYHA) Grade IV, any myocardial infarction/coronary event as well as any CNS-ischemic event and any thromboembolic event at any time < 6 months prior to Screening or presence of uncontrolled heart failure NYHA Grade III or higher.
7. Left ventricular ejection fraction (LVEF) < 50% as measured by an echocardiogram (ECHO) or multigated acquisition (MUGA) scan if ECHO cannot be performed at site for any reason.
8. QT interval corrected for heart rate using Fridericia's formula (QTcF) interval > 450 ms for men or > 470 ms for women.

9. Any active autoimmune disease that requires systemic immunosuppressive treatments, for which (re-)activation may present a medical threat to the subject as per Investigator's assessment.
10. Any history of non-infectious pneumonitis < 6 months prior to Screening.
11. Any active inflammatory bowel disease such as Crohn's disease or ulcerative colitis which are generally excluded or active autoimmunthyroiditis present < 6 months prior to Screening.
12. Type I diabetes.
13. History of CNS disease such as stroke, seizure, encephalitis, or multiple sclerosis (< 6 months prior to Screening).
14. Any history of motor neuron disorder or disease that affects motor neuron function.
15. Ongoing immune-related AEs (irAEs) and/or AEs \geq Grade 2 not resolved from previous therapies except vitiligo, stable peripheral sensory neuropathy up to Grade 2, hair loss, and stable endocrinopathies with substitutive hormone therapy.
16. Active allergy requiring systemic treatment (with the exception of histamine H1 receptor blocker treatment) or active infections requiring systemic anti-infectious therapy.
17. History of or clinical evidence of CNS primary tumors or metastases including leptomeningeal metastases, unless they have been previously treated, demonstrated no progression at least for 3 months before Screening, are asymptomatic and have had no requirement for steroids or enzyme inducing anticonvulsants in the last 14 days before Screening – subjects with suspected brain metastases at Screening should undergo a CT/MRI of the brain prior to study entry.
18. Systemic steroids at a daily dose of > 10 mg of prednisolone, > 2 mg of dexamethasone or equivalent, except non-systemic (inhaled, topical, nasal), for the last 28 days and ongoing.
19. Subjects with rapidly progressing disease (as per Investigator assessment), which may predispose to inability to tolerate treatment and/or study procedure.
20. Major surgery within last 4 weeks prior to Screening.
21. Known/expected hypersensitivity against CTL-002 and/or anti-PD-1/PD-L1 agents or their ingredients or previously had a severe hypersensitivity (\geq Grade 3) reaction to treatment with monoclonal antibodies (including pembrolizumab, nivolumab, cemiplimab etc.) and/or any of their excipients.
22. Evidence for active infection with human immunodeficiency virus (HIV), hepatitis B virus (HBV), hepatitis C virus (HCV), tuberculosis (TB), or severe acute respiratory syndrome coronavirus 2 (SARS-CoV-2) as per adequate testing performed.
23. Dementia or altered mental status that would prohibit informed consent.
24. Any other diseases, metabolic dysfunction, physical examination finding, or clinical laboratory abnormality giving reasonable suspicion of a disease or condition that in the opinion of the Investigator would contraindicate the use of an investigational drug.
25. Receipt of any organ transplantation, including hematopoietic cell transplantation, but with the exception of transplants that do not require immunosuppression (e.g., corneal transplant, hair transplant).

26. Paraneoplastic syndrome (PNS) of autoimmune nature, requiring systemic treatment (systemic steroids or immunosuppressive agents) or a clinical symptomatology suggesting worsening of PNS.
27. Vaccine administration within 4 weeks of investigational drug administration (exception: coronavirus disease 2019 [COVID-19] vaccination). Vaccination with live vaccines while on trial is prohibited. Administration of inactivated vaccines like inactivated influenza vaccines or RNA-vaccines is allowed, including COVID-19.
28. Known active drug or alcohol abuse.

3.3. Discontinuation of Study Treatment and Subject Withdrawal Criteria

Subjects are at any time free to withdraw from the study, without prejudice to further treatment (withdrawal of consent). Such subjects will always be asked about the reason(s) and the presence of any AEs. If possible, they will be seen by an Investigator and undergo the End of Treatment Visit (see [Section 6.1.9](#)) and assessments and procedures scheduled for the follow-up (see [Section 6.1.11](#)). Adverse Events should be followed up (see [Section 7.2.1](#)). More detailed guidance on Dose Modification and Discontinuation criteria is given in [Section 5.3](#).

Subjects must be discontinued from the study in the following situations:

1. Occurrence of any AEs that are deemed to be clinically significant in the opinion of the Investigator and/or the SRC and warrant that a subject must discontinue treatment and be withdrawn from the study.
2. DLT in Part A (Phase 1; dose escalation).
3. Severe non-compliance to this protocol as judged by the Investigator and/or the SRC.
4. Confirmed disease progression.
5. Subjects incorrectly initiated on CTL-002 or the defined checkpoint inhibitor.
6. Use of prohibited concomitant drug, as defined in [Section 5.4.3](#).
7. Pregnancy.
8. Withdrawal of consent.
9. Participation in any other clinical trial.

3.4. Procedures for Handling Subjects Incorrectly Initiated on CTL-002 and/or the Defined Checkpoint Inhibitor

Subjects who fail to meet the inclusion/exclusion criteria should not, under any circumstances, be enrolled to receive study medication. There can be no exceptions to this rule.

Where subjects who do not meet the inclusion criteria and have been enrolled or started treatment with CTL-002 (or the defined checkpoint-inhibitor) in error, the Investigator shall inform the Medical Monitor and the SRC immediately. The Investigator will discuss with the SRC and the subject the best way forward and whether study treatment should be aborted or continued. The decision making has the intent to provide the subject with the best possible solution for his/her situation. The Investigator and Medical Monitor are to ensure that all such decision making is appropriately documented.

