1.10. Trial Endpoints

1.10.1. Primary Endpoints

Part A (Phase 1; dose escalation):

- Evaluation of the number of subjects with AEs, including serious adverse events (SAEs), clinical laboratory data, vital signs, electrocardiograms (ECGs), physical examination (including neurological assessment) and Eastern Cooperative Oncology Group (ECOG) performance status

Determination of DLTs and maximum tolerated dose (MTD) in Part A of the study using the National Cancer Institute Common Terminology Criteria for Adverse Events (NCI-CTCAE) Version 5.0

Part B (Phase 2a; expansion):

- Evaluation of the clinical efficacy according to Response Evaluation Criteria in Solid Tumors (RECIST) V1.1 of CTL-002 in combination with an anti-PD-1 checkpoint inhibitor by assessment of:
 - The proportion of subjects with tumor shrinkage, a confirmed partial response (PR) and/or complete response (CR), and overall response rate (ORR)
 - The interval between the date of first CTL-002 administration and first documented evidence of a PR or CR (time to response [TTR])
 - The interval between the date of first documented evidence of PR or CR, until first documented evidence of disease progression or death, due to any cause (duration of response [DOR])
 - The interval between the date of first CTL-002 administration and the earliest date of disease progression or death (progression free survival [PFS])
 - The interval between the date of first CTL-002 administration and date of death due to any cause (overall survival [OS])
- Evaluation of the number of subjects with AEs, including SAEs, clinical laboratory data, vital signs, ECGs, physical examination (including neurological assessment), and ECOG performance status

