2.4. Follow-up

Following the Safety Follow-up Visit / End of Core Study Visit, subjects will be followed up with an Efficacy and Survival follow-up for response duration and survival every 3 months for 12 months (in Part A) and every 3 months for 24 months (in Part B). The follow-up will be performed by telephone contact or (e)mail.

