6.1.11. Follow-up

Time-point: Every 3 months (± 2 weeks) e.g., by phone/email for a total of 12 months in Part A (Phase 1; dose escalation) and a total of 24 months in Part B (Phase 2a; expansion).

- AEs (related to CTL-002 or study procedures)
- Concomitant medications (anti-cancer medication or due to related AEs)
- Cutaneous tumor lesion assessment/photography according to site practices
- Tumor assessment/Imaging: CT/MRI/PET-Scan according to local practice

- Survival

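### Section 3.3 takes subjects out of the study at progression and other events, which contradicts the planned survival follow-up and puts Part B overall survival at risk

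*Protocol*

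**What the plan says.** Section 3.3 contains one mandatory list of nine items, introduced by "Subjects must be discontinued from the study in the following situations". Item 4 is "Confirmed disease progression" and item 9 is "Participation in any other clinical trial". Item 1 concerns significant adverse events, after which a subject "must discontinue treatment and be withdrawn from the study". The other items are a dose-limiting toxicity in Part A, severe non-compliance, treatment started in error, prohibited medication, pregnancy and withdrawal of consent.

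The paragraph before the list covers subjects who withdraw consent. It asks that, if possible, they attend the End of Treatment Visit and have the "assessments and procedures scheduled for the follow-up". Nothing comparable is said for subjects whom the list removes.

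Other parts of the protocol describe a follow-up that continues after treatment:

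- **Section 1.10.1** places OS, from first CTL-002 dose to death from any cause, among the Part B primary endpoints. In Part A it is secondary (Section 1.10.2).
- **Section 2.4** says that after the Safety Follow-up Visit "subjects will be followed up with an Efficacy and Survival follow-up for response duration and survival every 3 months". The planned length is 24 months in Part B and 12 months in Part A. Section 6.1.11 lists survival among the data collected.
- **Section 9.5** defines the end of the study by the last subject's completion of that follow-up.
- **Synopsis, Duration of Treatment** lets treatment run to progression or withdrawal, and then describes the End of Treatment Visit, the Safety Follow-up Visit and up to 24 months of follow-up in Part B.

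**The concern.** Subjects are treated until progression, so progression is an expected route into survival follow-up. Section 3.3, read as written, says that a subject with confirmed progression must already have left the study. The two instructions cannot both be followed for the same subject.

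Sites applying Section 3.3 literally would end contact at progression, at toxicity, at non-compliance or at entry into another trial. Several of these events are related to the risk of death. Kaplan-Meier estimation assumes that censored subjects have the same future risk as those still followed. Here the censored subjects would on average be the sicker ones, so estimated survival would be too high. With up to 22 sites planned for Part B, different readings at different sites are a realistic possibility.

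**Working it through.** **Is there a figure to reproduce?** No. The protocol gives no OS assumption, event count or power. Part B cohort sizes rest on response rates alone. For example, with 14 subjects and a true rate of 20%, P(at least 2 responses) = 1 − 0.8^14 − 14 × 0.2 × 0.8^13 = 1 − 0.044 − 0.154 = 0.802, which matches the stated 80%. The check on OS is therefore a comparison of text.

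| Question | Section 3.3 | Elsewhere in the protocol |
|---|---|---|
| Subject with confirmed progression | Must leave the study (item 4) | Followed for survival with no exclusion (2.4, 6.1.11); treatment may go on past initial progression (4.6) |
| Subject started in error | Must leave the study (item 5) | Treatment may be stopped or continued (3.4) |
| Subject who joins another trial | Must leave the study (item 9) | Unapproved products barred only until long-term follow-up begins (5.4.3) |
| When participation ends | At the listed event | When survival follow-up is complete (9.5) |

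**Does study here simply mean treatment?** The evidence points both ways.

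- *Against:* item 1 names stopping treatment and leaving the study as two acts. The section heading does the same. Section 8.3.1 counts drug discontinuation and study discontinuation separately. Section 5.4.3 calls long-term follow-up a part of the study, so leaving the study would mean leaving follow-up.
- *For:* the synopsis uses withdrawal from the study for what ends treatment, and still sends those subjects to follow-up.

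The text does not settle the question.

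**What happens to OS under a literal reading?** Section 8.3.3, Table 10, censors living subjects at the date last known alive. If contact stops at the listed event, that date falls at or near the event, and the censoring depends on prognosis.

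**Direction of the bias.** The following inputs are assumed; none is in the protocol. Times are exponential, and every progressor is censored at progression. Let m be the median PFS, q the share of first PFS events that are deaths, and s the median survival after progression (months). With λ = ln 2/m and μ = ln 2/s:

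- True OS at 12 months = e^(−12λ) + (1 − q) × λ/(λ − μ) × (e^(−12μ) − e^(−12λ))
- Kaplan-Meier value with progressors censored = e^(−12qλ)

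For m = 2, q = 0.1, s = 6: λ = 0.3466 and μ = 0.1155. True OS = 0.0156 + 0.9 × 1.5 × (0.2500 − 0.0156) = 0.332. The censored estimate is e^(−0.416) = 0.660. A simulation of 200,000 subjects per scenario with 24 months of follow-up gave:

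| m | q | s | True 12-month OS | Estimate with progressors censored | Share of deaths observed |
|---|---|---|---|---|---|
| 2 | 10% | 6 | 0.330 | 0.656 | 11% |
| 2 | 20% | 6 | 0.296 | 0.435 | 22% |
| 2 | 10% | 10 | 0.487 | 0.661 | 13% |
| 4 | 10% | 8 | 0.536 | 0.814 | 12% |
| 4 | 20% | 8 | 0.492 | 0.664 | 24% |

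The estimate is too high in every row. This is an extreme case, with literal application at every site. It supports the direction of the bias and is not a forecast for this trial.

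**The case against.** The strongest reply is that one loosely worded sentence stands against a consistent follow-up plan. Besides the synopsis and Sections 2.4, 6.1.11 and 9.5, the follow-up visit records anti-cancer medication, which mainly makes sense after progression. Section 7.2.5 provides a dedicated form for death from progressive disease. Section 8.3.2 flags adverse events that occur after further cancer therapy. Even subjects who withdraw consent are asked to attend follow-up if possible. Item 9 can be read as applying only during active participation. All of this stands, and it shows that the sponsor intends to follow these subjects. It does not remove the contradiction, because Section 3.3 is the section that tells sites when a subject leaves.

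Two of the nine items lend little support. The dose-limiting toxicity item applies only to Part A, where OS is secondary. Withdrawal of consent can properly end data collection.

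The consequence is also bounded. The study is exploratory with no formal comparisons (Section 8.1), and cohort expansion turns on response. OS is one of several primary endpoints in Part B.

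**Conclusion.** The contradiction is real and should be corrected. It puts a Part B primary endpoint at risk of informative censoring, with upward bias in Kaplan-Meier OS wherever a site follows Section 3.3 literally. The size cannot be stated: it depends on how many sites do so and on PFS and OS, for which the protocol gives no assumptions.

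A reader might infer more than the documents support:

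- *That the protocol censors OS at progression.* It does not. Table 10 censors at the date last known alive, and several sections plan contact after progression.
- *That all progressors, or a fixed share of survival time, will be lost.* No median is given from which to calculate such a share. Item 4 also refers to confirmed progression, and Section 6.2.5.1 places reassessment 4 to 8 weeks after the scan that raised it, so any loss of contact would tend to come later than the PFS date.
- *That DOR and PFS are cut short by design.* Section 6.2.5.1 allows response assessments until the end of Efficacy and Survival follow-up. They would be cut short only under the same literal reading.

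**What to change.** In Section 3.3, separate the end of treatment from the end of study participation. State that a subject who meets any listed criterion still completes the End of Treatment and Safety Follow-up Visits and enters Efficacy and Survival follow-up under Sections 2.4 and 6.1.11, unless the subject withdraws consent to follow-up.

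Merely replacing the word study with study treatment in the opening sentence is not enough. It would turn the list into a mandatory treatment-stopping rule and sharpen the conflict with Sections 4.6 and 3.4. The sponsor must separately reconcile item 4 with Section 4.6, item 5 with Section 3.4 and item 9 with Section 5.4.3. Which treatment rule applies is for the sponsor to settle.

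The follow-up change costs one or two sentences and adds no visits or assessments, because the follow-up is already scheduled.
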